## 7.3 Analysis Plan

Patients are expected to have on average four brain lesions each. The primary analysis will be performed on the largest lesion within patients at baseline, and secondary analyses will consider all lesions. The sensitivity of each method at detecting lesions as determined by T1 weighting will be reported with 95% confidence intervals. Analyses will also be performed at the subsequent scans as numbers permit.

For the secondary endpoints that consider treatment response, for each of the imaging methods, at each time point, we will calculate the contrast to noise ratio (CNR) in patients with lesions that respond to treatment and in patients with local failure and will compare these by using a Wilcoxon rank-sum test. If numbers permit, analyses may be repeated using all lesions. Additionally, of the lesions that initially respond, some will subsequently grow in size after the initial response. Of these, some will be considered treatment change and some residual disease. The CNR will be compared between lesions with treatment change and those that are progressive disease using a Wilcoxon rank-sum test.

All statistical tests will be performed with two-sided tests with 5% Type I error rates. No adjustment will be made for the multiplicity of testing. We recognize that the Type I error rate overall will be greater than 5%.

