### 1.2 Secondary Objectives

#### 1.2.1 Conspicuity:

- 1.2.1.1 Quantitative MRI: To assess the conspicuity of T2 imaging at detecting brain metastases on a per-patient basis at follow-up scans and on a per-lesion basis at baseline and at follow-up time points.
- 1.2.1.2 Chemical Exchange Saturation Transfer (CEST) MRI: To assess the conspicuity (CNR) of CEST imaging at detecting brain metastases on a per-patient basis at follow-up scans and on a per-lesion basis at baseline and at follow-up time points.
- 1.2.1.3 Multiple B Value Diffusion Imaging (Adv Diff): To assess the conspicuity (CNR) of Adv Diff at detecting brain metastases on a per-patient basis at follow-up scans and on a per-lesion basis at baseline and at follow-up time points.
- 1.2.1.4 Gradient- and Spin-Echo (GESE) Dynamic Susceptibility Contrast (DSC) perfusion imaging: To assess the conspicuity of GESE DSC and standard Gradient Echo (GE) DSC at detecting brain metastases on a per-patient basis at follow-up scans and on a per-lesion basis at baseline and at follow-up time points.

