Current MR imaging protocols for brain metastasis evaluation rely on contrast-enhanced T1-weighted MRI (CE-T1WI), which has proven itself a valuable tool for the visualization of tumor margins. However, changes in lesion size as determined by CE-T1WI images taken alone are not specific to cell death. There has been more success with quantitative MR methods, such as the apparent diffusion coefficient (ADC), which increases with apoptosis and has been correlated with response to therapy. It has also been shown that low pretreatment ADC values are correlated with a favorable response. However, given that ADC is sensitive to many changes in tissue micro-structure, it is often difficult to distinguish between tumor necrosis, edema, or

radiation-induced inflammation, which inhibits its use in monitoring cancer treatment.

Advanced imaging techniques currently in clinical use such as dynamic contrast enhancement perfusion imaging and dynamic susceptibility contrast perfusion imaging have been shown to improve diagnostic accuracy in the assessment of brain metastasis behavior following stereotactic radiosurgery. However, their diagnostic yield is not ideal (sensitivity and specificity less than 90% in clinical trial settings) and their usage is demonstrated in the reactionary scenario following the development of abnormal conventional imaging. These techniques have not been shown to be able to predict future behavior of lesions prior to the development of anatomic imaging abnormalities.

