## 2.7 Protocol Particular Disease Description

Brain metastasis will be defined as a three-dimensional intraaxial enhancing abnormality on MR imaging in a patient with pathology-proven extracranial non-central nervous system malignancy.

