# Proprietary Information of MD Anderson

Protocol No: 2019-1008

Version No: 04

Version Date: August 31, 2021

Disease **recurrence** will be determined by surgical pathology (if available) or at least three months of imaging follow-up. Imaging findings will be considered recurrent disease in a lesion if:

1. The lesion was originally considered to be a treatment responder.
2. The lesion showed a successive increase in the size of 25% from nadir or a single imaging time point increase of 40%. (see section 5.1)

Lesions that show an increase in size, but do not meet these criteria will be considered radiation necrosis.

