## 7.2 Sample Size

For each of the primary conspicuity endpoints, the objective is to estimate the ability of each imaging method (T2 weighted MRI, CEST MRI, Adv Diff, and DESE DSC) at identifying brain metastases at baseline. Standard of care qualitative T1 post-contrast imaging will be considered the gold standard. Each patient will have between 1 and 10 lesions, with an expected average of 4 lesions per patient. (For patients with more than 10 lesions, 10 will be chosen as described in Section 5.1.4.1.) The primary analysis will consider the largest lesion within each patient, and the analysis will be repeated considering all lesions. The sensitivity will be calculated along with the corresponding 95% confidence interval. With 50 patients, this confidence interval will be no wider than 14.5% on either side of the estimated proportion. The confidence interval around the proportion of total lesions detected will be tighter, depending on the total number of lesions.

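### Follow-up sensitivity is measured against T1 imaging alone, so after radiosurgery it is agreement with T1 enhancement rather than sensitivity for tumour

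*Combined protocol and SAP*

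**What the plan says.** - **Reference.** Section 7.2, in a paragraph on the baseline endpoints, states: "Standard of care qualitative T1 post-contrast imaging will be considered the gold standard". Section 7.3 states: "The sensitivity of each method at detecting lesions as determined by T1 weighting will be reported with 95% confidence intervals".
- **Extension to follow-up.** The next sentence of 7.3 is "Analyses will also be performed at the subsequent scans as numbers permit". It names no different reference. Section 4.5 places the baseline scan before radiation and adds seven later scans.
- **Target.** Section 1.2.1 describes the secondary conspicuity objectives as assessing each method "at detecting brain metastases on a per-patient basis at follow-up scans and on a per-lesion basis at baseline and at follow-up time points".
- **Definition of metastasis.** Section 2.7: "Brain metastasis will be defined as a three-dimensional intraaxial enhancing abnormality on MR imaging". No condition on viability or treatment status is attached.
- **Necrosis.** Section 1.2.2 sets separation of radiation necrosis from progressive disease as an objective for CEST, Adv Diff, GESE DSC and Adv ASL. Section 7.1 bases recurrence on pathology or on size rules over imaging follow-up, and then adds: "Lesions that show an increase in size, but do not meet these criteria will be considered radiation necrosis".
- **Limits of contrast T1.** Section 2.1 says that "changes in lesion size as determined by CE-T1WI images taken alone are not specific to cell death".

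**The concern.** At baseline the lesions are untreated and awaiting radiation, so T1 post-contrast imaging is a reasonable reference for presence of metastasis. After radiosurgery the same reference takes in tumour and radiation necrosis together, and the protocol treats telling these apart as a main reason for the new methods.

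CEST, Adv Diff and GESE DSC are therefore judged twice at follow-up on criteria that can conflict. A map that is negative in an enhancing necrotic lesion does what 1.2.2 hopes for, yet against a T1 reference that lesion counts as not detected. A map that is positive in every enhancing lesion, necrotic or not, scores well. The necrosis label is used only in the 7.3 rank-sum comparison of CNR; it is not linked to the sensitivity calculation.

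A follow-up result reported as sensitivity for brain metastases could thus favour the less specific method.

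**Working it through.** **The plan's own figure.** Section 7.2 says that with 50 patients the 95% confidence interval extends at most 14.5 points either side. The exact (Clopper-Pearson) interval at 25/50 runs from 35.5% to 64.5%, a half-width of 14.47 points. The figure reproduces and is not in dispute. The issue is what the proportion estimates.

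**Model.** Among lesions positive on the T1 reference at follow-up, let
- w = share without viable tumour,
- Se = share of viable lesions the method calls positive,
- f = share of non-viable lesions the method calls positive.

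Apparent sensitivity = (1−w)·Se + w·f, so its bias against Se is w·(f − Se): negative when f < Se, positive when f > Se.

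**Inputs.** The documents give no value for w, Se or f. I assume Se = 90% and show w = 10%, 25% and 50% with f at its two extremes.

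| w | Tumour-specific, f = 0 | Bias | Non-specific, f = 100% | Bias |
|---|---|---|---|---|
| 10% | 0.90×0.90 = 81% | −9 points | 0.81 + 0.10 = 91% | +1 point |
| 25% | 0.75×0.90 = 67.5% | −22.5 points | 0.675 + 0.25 = 92.5% | +2.5 points |
| 50% | 0.50×0.90 = 45% | −45 points | 0.45 + 0.50 = 95% | +5 points |

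At w = 25% the shortfall of 22.5 points is larger than the planned 14.5-point half-width.

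**Ranking of methods.** Compare a tumour-specific method (Se = 90%, f = 0) with a less sensitive, non-specific one (Se = 80%, f = 100%). The order reverses when 0.9(1−w) < 0.8(1−w) + w, that is 0.1 < 1.1w, or w above about 9%. At w = 25% the readings are 67.5% against 0.75×0.80 + 0.25 = 85%.

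**Cost in precision.** Suppose one lesion per patient, all 50 patients scanned, and only viable lesions counted. Then n is 45, 38 (37.5 rounded) or 25 at the three values of w, and the largest exact half-width is 15.3, 16.6 or 20.4 points.

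**The case against.** The strongest reply is that the plan already says what it measures. Section 2.7 defines metastasis by enhancement, and 7.3 refers sensitivity to lesions determined by T1. On that reading the figure is openly agreement with T1, and tumour versus necrosis is handled by the separate CNR comparison. This largely stands as a description of the calculation. It does not settle the label: 1.2.1 still reports the result as detection of metastases, while 1.2.2 and 7.1 divide the same lesions into disease and necrosis.

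Several stronger readings are tempting, and the documents do not support them:
- *The plan scores a negative map in necrosis as a miss.* No positivity threshold or reader rule is given for any study method. The miss follows from the definition of sensitivity once some rule is chosen.
- *The denominator shrinks from scan to scan as lesions respond.* No such rule is stated. Section 5.1.4.1 speaks of tracking selected lesions, which fits a fixed baseline set at least as well. What happens to a lesion that no longer enhances is unspecified.
- *The bias is always downward.* It runs both ways, and a non-specific method gains.
- *Section 2.1 shows that enhancement is an invalid reference.* That sentence concerns change in size, not visibility, and supports the point only indirectly.
- *The tumour and necrosis classes are already available for every lesion.* Section 7.1 labels necrosis only in lesions that grow.

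It is also fair that the gold-standard sentence belongs to a baseline paragraph, so its use at follow-up is inferred. No alternative is offered, however, and if one is intended it should be stated. Finally, the affected analyses are secondary, descriptive and conditional on numbers.

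**Conclusion.** The point holds for the secondary follow-up conspicuity analyses only. The primary baseline analysis precedes radiation and is untouched. As written, the follow-up figure estimates agreement with T1 enhancement. Read as sensitivity for tumour, it understates a tumour-specific method and overstates one that also shows necrosis. Under the assumed Se of 90%, the error is 9 to 45 points downward for f = 0 and 1 to 5 points upward for f = 100%, as w goes from 10% to 50%.

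The direction of each error needs only f below or above Se. The sizes rest on assumed values and are not predictions for this trial. The conclusion also takes T1 in 7.3 to mean post-contrast T1, which 7.2 and 2.7 support.

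**What to change.** In section 7.3:
1. Call the pooled follow-up figure *agreement with T1 post-contrast enhancement*, not sensitivity for metastasis, and align 1.2.1.
2. Tabulate detection separately by lesion status: recurrence (by pathology or imaging follow-up); radiation necrosis (growth after response that does not meet the recurrence criteria); responder without regrowth; and treatment failure (never responded). Treatment failure needs its own row because 7.1 contradicts itself: a growing lesion that never responded is a failure under the response definition, but, read literally, radiation necrosis under the recurrence definition, since it cannot meet the first recurrence criterion. The two definitions must be reconciled.
3. Report the number of baseline-tracked lesions that no longer enhance, with the study method's result, as a separate count outside the sensitivity denominator. Including them would mark down a correctly negative map in a lesion that has fully responded.

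The change needs SAP wording and one table, with no new scans or patients. The drawback is small numbers per row and correspondingly wide intervals.

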## 1 OBJECTIVES

### 1.1 Primary Objectives

#### 1.1.1 Conspicuity:

- 1.1.1.1 Quantitative MRI: To assess the conspicuity of idealized T1 and T2 imaging at detecting brain metastases at baseline.
- 1.1.1.2 Chemical Exchange Saturation Transfer (CEST) MRI: To assess the conspicuity (CNR) of CEST imaging at detecting brain metastases at baseline.
- 1.1.1.3 Multiple B Value Diffusion Imaging (Adv Diff): To assess the conspicuity (CNR) of Adv Diff at detecting brain metastases at baseline.
- 1.1.1.4 Gradient- and Spin-Echo (GESE) Dynamic Susceptibility Contrast (DSC) perfusion imaging: To assess the conspicuity of GESE DSC and standard Gradient Echo (GE) DSC at detecting brain metastases at baseline.

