#### 1.2.2 Treatment Response:

- 1.2.2.1 Quantitative MRI: To assess the trend of idealized quantitative T1 and T2 values of brain metastases compared to normal brain parenchyma following treatment with stereotactic radiosurgery.
- 1.2.2.2 Chemical Exchange Saturation Transfer (CEST) MRI: To assess the ability of CEST imaging to differentiate radiation necrosis from progressive disease in brain metastases following stereotactic radiosurgery.

- 1.2.2.3 Multiple B Value Diffusion Imaging (Adv Diff): To assess whether Adv Diff can differentiate radiation necrosis from progressive disease in brain metastases following stereotactic radiosurgery.
- 1.2.2.4 Gradient- and Spin-Echo DSC perfusion imaging: To assess whether GESE DSC improves differentiation of radiation necrosis from progressive disease in brain metastases following stereotactic radiosurgery compared to standard GE DSC.
- 1.2.2.5 Multiple inversion time (TI) arterial spin labeling (ASL) “Adv ASL” perfusion imaging: To assess the ability of Adv ASL to differentiate radiation necrosis from progressive disease in brain metastases following stereotactic radiosurgery.

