# **7 STATISTICAL CONSIDERATIONS**

## **7.1 Definitions**

Brain metastases “**treatment response**” will be defined by size and contrast to noise ratio (CNR).

Size – treatment response in a lesion will be considered as a decrease in size of 30%. (see section 5.1)

CNR—treatment response will be considered as a decrease in T1 post-contrast CNR of at least 20% (see section 5.2) by standard T1 post contrast imaging for a lesion.

Metastases that do not meet these criteria for treatment response will be considered treatment failure.

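### Section 7.3 tests only CNR, but no noise ROI is specified for Adv Diff, GESE DSC or Adv ASL, and the GESE-versus-GE objective has no comparison

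*Combined protocol and SAP*

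**What the plan says.** Section 7.3 sets out two secondary contrasts, both by rank-sum test and both on CNR. The first is responders versus local failures: "For the secondary endpoints that consider treatment response, for each of the imaging methods, at each time point, we will calculate the contrast to noise". The second concerns lesions that respond and later grow: "The CNR will be compared between lesions with treatment change and those that are progressive disease using a Wilcoxon rank-sum test".

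Four objectives in section 1.2.2 ask about radiation necrosis versus progressive disease. They cover CEST (1.2.2.2), Adv Diff (1.2.2.3: "To assess whether Adv Diff can differentiate radiation necrosis from progressive disease in brain metastases following stereotactic radiosurgery"), GESE DSC (1.2.2.4) and Adv ASL (1.2.2.5: "To assess the ability of Adv ASL to differentiate radiation necrosis from progressive disease in brain metastases following stereotactic radiosurgery"). Objective 1.2.2.4 is comparative: "To assess whether GESE DSC improves differentiation of radiation necrosis from progressive disease in brain metastases following stereotactic radiosurgery compared to standard GE DSC". Objective 1.2.2.1, on Quantitative MRI, is about a trend ("To assess the trend of idealized quantitative T1 and T2 values of brain metastases compared to normal brain parenchyma") and is not one of the four.

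The measurements are in section 5. An extracranial noise ROI appears in 5.2.4 (standard T1), 5.3.4 (Quantitative MRI) and 5.4.4 (CEST). Sections 5.5 to 5.8 contain none.

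**The concern.** A CNR needs a noise term. If 7.3 is followed literally, the data sheet for three of the five study methods lacks one of its ingredients, and the quantities that are recorded are not named anywhere in section 7. Someone then has to decide what to test in place of CNR, and the plan does not say what or when.

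The GESE objective has a second gap. Both rCBV values are to be read on the same lesion, so the paired data will exist. Section 7.3, however, compares only groups of lesions within a method. Carried out as written, the plan would finish without an answer to 1.2.2.4.

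**Working it through.** **Plan's own figure.** The only precision figure in section 7 is 14.5% for 50 patients. The exact (Clopper-Pearson) 95% interval at 25/50 has limits Beta(0.025; 25, 26) and Beta(0.975; 26, 25), and a half-width of 0.1447, which rounds to 14.5%. The simple normal formula gives 1.96 × √(0.25/50) = 0.139. The figure reproduces with the exact interval. It concerns primary sensitivity and does not depend on CNR.

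**Measurements against the test variable.**

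| Method | Section | Recorded | Noise ROI | Necrosis v progression objective |
|---|---|---|---|---|
| Quantitative MRI | 5.3 | lesion, background, noise | yes | none (1.2.2.1 is a trend) |
| CEST | 5.4 | lesion, background, noise | yes | 1.2.2.2 |
| Adv Diff | 5.5 | AKC and ADC, lesion and background | no | 1.2.2.3 |
| GESE DSC | 5.6, 5.7 | rCBV on GESE and on GE; lesion vessel size | no | 1.2.2.4 |
| Adv ASL | 5.8 | CBF, lesion and background; BAT | no | 1.2.2.5 |

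This gives 3 of 5 methods without a noise ROI, and 3 of the 4 necrosis-versus-progression objectives. I take treatment change in 7.3 to mean radiation necrosis in 1.2.2 and 7.1.

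**Could section 5.2 serve every method?** Its title is general, but its steps use T1 post-contrast imaging. Section 7.1 cites it for that purpose: response "will be considered as a decrease in T1 post-contrast CNR of at least 20% (see section 5.2) by standard T1 post contrast imaging". Sections 5.3 and 5.4 each restate their own noise ROI, which a common template would make unnecessary. The outputs in 5.5 to 5.8 are derived parameters, and rCBV is already expressed relative to white matter. A lesion-to-background ratio can be formed for several of them, but it is not a CNR and the plan does not propose it.

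**Would 7.3 answer 1.2.2.4?** Suppose GE and GESE count as separate methods, each with its own rank-sum test. Each p-value then addresses whether that map separates the two lesion groups. Neither addresses whether one map separates them better. That question needs a within-lesion comparison, for example AUC(GESE) − AUC(GE), whose variance is Var(GESE) + Var(GE) − 2·Cov.

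**Precision of that difference (illustrative).** The documents give no count of lesions that respond and then regrow, no AUC and no GESE-GE correlation. Assumptions: both AUCs 0.70, so the groups are √2 × Φ⁻¹(0.70) = 1.414 × 0.524 = 0.74 SD apart; normal values; correlation 0.5 to 0.9; independent lesions. The half-width is 1.96 × SE of the difference, by simulation:

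- 10 v 10 to 25 v 25 lesions: SE about 0.037 to 0.124, half-width about 0.07 to 0.24.
- 4 v 4 to 8 v 4 lesions: SE about 0.097 to 0.224, half-width about 0.19 to 0.44.

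The plan expects an average of four lesions per patient. Lesions in one patient are unlikely to be independent, so the interval should be computed at patient level.

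**The case against.** Several points on the other side stand.

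- Section 7.3 clearly intends a rank-sum test for every method. For Adv Diff and Adv ASL the defect is therefore an unspecified test variable, not a missing analysis. The variable could still be fixed before anyone looks at the data.
- No CNR formula is written for any method. The defensible count is that a noise ROI is missing for three of five methods, not that CNR is fully defined for the other two.
- These are secondary analyses. Section 7.3 openly makes no multiplicity adjustment and accepts an overall error rate above 5%. That covers the number of tests; it does not say what is tested.
- A reader might infer that the investigators would call GESE superior if its test were significant and the GE test were not. The plan states no such rule. The point is that no comparison is planned.

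A reader might also infer that the primary endpoint for Adv Diff fails, because objective 1.1.1.3 is "To assess the conspicuity (CNR) of Adv Diff at detecting brain metastases at baseline" and 5.5 has no noise ROI. The documents do not support that. The primary analysis is a sensitivity, and neither 7.2 nor 7.3 says how a lesion counts as detected on a method. If detection rests on CNR, the Adv Diff endpoint is affected; if it rests on a visual reading, it is not. For the same reason the documents do not show that it is unaffected.

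**Conclusion.** The point holds for the secondary treatment-response analyses and should be fixed before analysis. The test variable in 7.3 does not match what section 5 records for 3 of 5 methods, and this touches 3 of the 4 necrosis-versus-progression objectives. Objective 1.2.2.4 has no analysis that could answer it, although 5.6.2 collects the paired data. These conclusions come from comparing the sections and rest on no assumed number.

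No size of bias or error is claimed. The half-widths above depend on assumed lesion counts, AUC, correlation and independence, and serve only to show how imprecise a GESE-GE comparison may be. The effect on the Adv Diff primary endpoint cannot be settled from the documents.

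**What to change.** Amend 7.3 before analysis.

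1. **Objective 1.2.2.4.** Compare GESE rCBV with GE rCBV on the same lesions by the paired difference in AUC for necrosis versus progression, with a 95% CI. Use a patient-level (cluster) bootstrap when patients contribute more than one lesion. Report it as an estimate, if numbers permit. Vessel size is supporting.
2. **Adv Diff and Adv ASL.** Replace CNR with a quantity that section 5 already records, one lead variable per method, chosen by the study team. Examples are the lesion-to-white-matter ratio of AKC and that of CBF. Keep the rank-sum test and treat ADC and BAT as supporting.

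The 5.2 CNR with its 20% criterion, the CNR analyses for Quantitative MRI and CEST, and the 14.5% calculation need no change for this point.

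The cost is wording. The lesion and background values needed are already to be measured, so no new scans or ROI readings are required. There are two downsides: the non-lead parameters become supporting only, and the AUC difference may be too imprecise to settle whether GESE is better, especially if few lesions regrow.

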## 3.3 NUMBER OF PARTICIPANTS

Fifty (50) patients will be studied.

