## 4.5 Imaging Time Points

- 4.5.1 The baseline study scan will be performed within the fourteen (14) days **before** scheduled brain radiation treatment.
- 4.5.2 Seven additional study scans will be performed on the schedule of the patient's clinical protocol, but not less than four (4) weeks apart and not more than 16 (sixteen) weeks apart.

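### The follow-up comparisons in 7.3 ignore the same lesion's pre-radiosurgery value, so a post-treatment difference cannot be told from one already present at baseline; a baseline-adjusted analysis should be reported beside the raw test

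*Combined protocol and SAP*

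**What the plan says.** Section 7.3 handles the treatment-response endpoints method by method: "at each time point, we will calculate the contrast to noise ratio (CNR" in patients whose lesions respond and in patients with local failure, and the investigators "will compare these by using a Wilcoxon rank-sum test". For lesions that respond and later grow, "The CNR will be compared between lesions with treatment change and those that are progressive disease", again by rank-sum test. "All statistical tests will be performed with two-sided tests with 5% Type I error rates", with no multiplicity adjustment. No change from baseline, baseline covariate or longitudinal model is named.

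A baseline value exists. Section 4.5 states "The baseline study scan will be performed within the fourteen (14) days" before radiation, and Section 4.3 lists quantitative MRI, CEST, Adv Diff, GESE DSC and Adv ASL for all patients. Baseline imaging is also a primary objective, for example "To assess the conspicuity (CNR) of CEST imaging at detecting brain metastases at baseline".

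Section 7.1 does use a within-lesion decrease in CNR, but only to define response, and only for standard T1 post-contrast imaging.

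**The concern.** Responders and failures are defined by outcome, so nothing balances their baseline values. Any solid-organ primary is eligible (Section 3.1). Section 2.1 reports that low pretreatment ADC goes with a favourable response and that ADC rises with apoptosis. On that account responders start lower and then rise, so the two effects oppose each other in a raw follow-up comparison. For another marker they could reinforce each other.

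Either way, a p-value from the raw test at a follow-up scan does not show whether the marker behaved differently after radiosurgery. If baseline and follow-up values are correlated, the raw test also leaves removable between-lesion variation in the noise. The contralateral white-matter reference does not solve this: it is a reference within each scan, not the lesion's own starting value.

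**Working it through.** **The plan's own figure.** The only computed design figure is in 7.2: "With 50 patients, this confidence interval will be no wider than 14.5% on either side of the estimated proportion". The exact (Clopper-Pearson) interval at 25/50 is 35.53% to 64.47%, a half-width of 14.47 points. The figure reproduces and is untouched by this point. No power is stated for the comparisons in question.

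**Inputs from the documents.** "Fifty (50) patients will be studied" (3.3); two-sided 5% tests and the rank-sum test (7.3).

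**Assumptions, not in the documents.** 35 responders and 15 failures, all still scanned; normal values with SD 1; baseline-to-follow-up correlation ρ from 0 to 0.8.

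**Step 1: what the raw test sees.** Let b be the baseline gap between groups and d the follow-up difference between lesions with the same baseline value, both in SD. The expected raw follow-up difference is d + ρb. With ρ = 0.7:
- d = 0, b = 0.5: raw difference 0.35, although nothing differs given baseline.
- d = 0.8, b = −0.5: raw difference 0.45, so much of the effect is masked.
- d = 0.5, b = 0.5: raw difference 0.85, with the baseline gap counted as signal.

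**Step 2: power with equal baselines, analytic.** Adjustment multiplies the variance by 1 − ρ². With rank efficiency 3/π, the standard error is √[(1/35 + 1/15)/(3/π)] = √(0.0952/0.955) = 0.316.
- Raw: 0.8/0.316 = 2.53; Φ(2.53 − 1.96) = 72%.
- Adjusted: dividing 2.53 by √0.91, √0.75 and √0.51 gives 2.66, 2.93 and 3.55, hence 76%, 83% and 94% for ρ = 0.3, 0.5 and 0.7.
- A plain change score multiplies the variance by 2(1 − ρ), that is 1.4, 1.0 and 0.6, giving 57%, 72% and 91%. It loses power when ρ is below 0.5.

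**Step 3: simulation.** 4,000 trials per setting, 35/15; percentage of trials rejecting, raw rank-sum / rank ANCOVA:

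| ρ | d = 0.8, b = 0 | d = 0, b = 0.5 | d = 0.8, b = −0.5 | d = 0.5, b = 0.5 |
|---|---|---|---|---|
| 0 | 69.6 / 69.1 | 5.2 / 5.4 | 69.0 / 66.7 | 33.0 / 31.5 |
| 0.3 | 68.3 / 71.6 | 6.9 / 3.8 | 50.2 / 69.1 | 50.5 / 34.8 |
| 0.5 | 68.2 / 79.1 | 11.8 / 5.6 | 38.7 / 75.6 | 63.1 / 41.4 |
| 0.7 | 69.3 / 92.5 | 18.7 / 5.0 | 28.5 / 87.9 | 74.7 / 56.1 |
| 0.8 | 68.6 / 97.1 | 24.0 / 5.0 | 23.0 / 96.4 | 78.6 / 68.4 |

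Separate simulations under the same assumptions gave adjusted power of 72% to 73%, 80% to 81% and 91% at ρ = 0.3, 0.5 and 0.7. The simulated figures are slightly below the analytic ones and are preferred here. With a 40/10 split and equal baselines, raw power is about 56%, against 60.0%, 67.3% and 81.1% adjusted.

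**Step 4: which baseline value exists.** Section 5 specifies the noise region that a CNR needs only for T1 post-contrast (5.2), quantitative MRI (5.3) and CEST (5.4). Adv Diff yields AKC and ADC, GESE DSC yields rCBV and vessel size, and Adv ASL yields CBF and BAT.

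**The case against.** The strongest reply is that the raw test answers a legitimate question. Four of the five treatment-response objectives in 1.2.2 ask whether imaging can separate radiation necrosis from progressive disease; only 1.2.2.1 asks about a trend. For single-scan separation a baseline gap may be real signal, and adjusting removes it: in the last column of the table at ρ = 0.7, raw power is 74.7% against 56.1% adjusted. This stands. A reader might infer that the raw test is wrong and should be replaced or demoted. The documents do not support that, because the two tests have different estimands.

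A reader might also infer that a baseline CNR is available for every method. Images are acquired for every method, but Section 5 does not define a CNR for Adv Diff, GESE DSC or Adv ASL, and Adv ASL has no baseline conspicuity objective. The adjustment has to use each method's own metric.

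Baseline is one of the imaging time points, so the plan's wording arguably includes a group comparison at baseline. That could reveal a gap, but it would not remove it from the follow-up comparisons.

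Finally, the power gain depends on an unknown correlation. It could be low: the quantitative weighting is the one that maximises lesion signal (5.3.2) and may differ between scans, and Section 2.2 notes that routine MR intensities have no consistent scale. At ρ = 0.3 the gain is only about 3 to 5 points. That too stands. It weakens the power argument more than the argument about baseline differences.

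**Conclusion.** The point holds as a gap in secondary analyses. With the raw test alone, a follow-up difference between these non-randomised groups cannot be separated from one present before treatment, and the protocol's background gives a reason to expect such a gap for at least ADC. Under the assumed 35/15 split and ρ of 0.3 to 0.7, a 0.5 SD baseline gap raises rejection from about 5% to about 7% to 19% when nothing differs given baseline. If the gap opposes a 0.8 SD difference, raw power falls to about 50% to 29%, against 69% to 88% adjusted. The gain in power with equal baselines is the lesser reason and is conditional on ρ; at ρ = 0 there is none.

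Three limits apply. The documents give no correlation, effect size or split, and patients may leave before a given scan (4.6), so these figures illustrate and do not predict. No calculation is offered for treatment change against progressive disease, because the number of lesions that respond and then grow is not stated. Detectable differences from the normal-theory shortcut should not be quoted: (1.96 + 0.84) × √(1/35 + 1/15) gives about 0.86 SD, yet the simulated rank-sum test has only 76% to 77% power even at 0.87 SD.

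The primary sensitivity estimate and its precision are unaffected.

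**What to change.** In 7.3:

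- Keep the Wilcoxon rank-sum comparison at each time point, and label it as the analysis of whether a single scan separates the groups.
- Add, for each method and each follow-up scan, a co-reported rank-based ANCOVA with the same lesion's baseline value of the same metric as covariate, labelled as the analysis of post-treatment change. Do the same for treatment change against progressive disease. Use the baseline as a covariate, not only through a change score, which loses power when the correlation is below 0.5.
- Name the metric per method as Section 5 defines it: CNR for quantitative MRI and CEST; AKC and ADC for Adv Diff; rCBV and vessel size for GESE DSC; CBF and BAT for Adv ASL.
- Leave T1 post-contrast CNR out of the adjusted comparison. Its decrease is part of the response definition in 7.1, so the comparison would be circular.
- State that neither analysis replaces the other.

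The cost is analysis wording only, with no extra scan or patient. Lesions without a usable baseline value drop out of the adjusted analysis, so the number excluded should be reported. The additional tests also add to a multiplicity that the plan already leaves unadjusted.
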